Methods: This will be an open label, single-site, clinical research study. Up to 40 active duty military personnel, or recent Veterans, age 18 or older, who have been diagnosed with PTSD, have been treated for, are referred by military medical personnel for, or have active symptoms of military-related traumatic stress, with or without mild TBI, will be recruited to receive up to 24 HIRREM sessions over 2 weeks. The primary outcome will be differential change in the PCL-M from baseline to completion of HIRREM sessions. Secondary measures include differential change in the Insomnia Severity Index (ISI), the Center for Epidemiological Studies Depression Scale (CES-D), an anxiety measure (GAD-7), a quality of life measure (EQ-5D), an autonomic symptom measure (Compass 31), and a daily sleep diary, along with physiological measures including heart rate (HR), and blood pressure (BP), with calculation of heart rate variability measures (HRV), baroreflex sensitivity (BRS). Functional measures will include reaction time (drop-stick task), and grip strength (hydraulic dynamometer). If there is a history of TBI, a Rivermead Post-Concussion Symptoms Questionnaire (RPQ) will be added. There will be pre- and postintervention data collection for all measures (baseline, V1, and at completion of HIRREM sessions, V2). Self-report measures will be repeated by phone at 1, 3, and 6 months after completion of sessions (V3, V4, and V5 respectively). The sleep diary will be maintained from V1 until V3. A brainwave assessment will be obtained at V1.

Sample Size and Statistical Analysis: The primary statistical intent of this pilot clinical research study is to generate estimates of effect size in order to plan subsequent randomized studies. Given that outcomes will be collected at multiple follow-up time points (V2, V3, V4, and V5), effect estimates will be based on generalized linear models (GLM), which can accommodate within-subject correlations due to repeated assessment over time. While no directly relevant, controlled study data is currently available, a recent, national study of prolonged exposure therapy in veterans with PTSD (N=1,888) indicated a mean decrease on the PCL-M of 15.2 points (standard deviation = 20.0). Assuming a similar level of variability

in our population and a sample of 10 subjects, we expect to generate a 95% confidence interval for the mean change on the PCL-M with a half-width (1.96 x standard error) of \pm 12.4 points.

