- Autonomic symptoms will be evaluated with the Compass 31 inventory. We hope to see improved autonomic scores.
- The amount and quality of sleep as evaluated with a daily sleep diary, and with the ISI. The ISI allows pre- to post-HIRREM evaluation of insomnia, while the sleep diary allows evaluation of the timing and trajectory of any improvements in sleep. We expect to see improvement in the ISI, as well as parameters of the sleep diary.
- Reaction time, as evaluated by a drop-stick, clinical reaction time apparatus. We expect to see improved reaction time.
- Grip Strength, as evaluated by a hand dynamometer. We expect to see improved grip strength.
- Brain pattern as evaluated by analysis of electrical frequency and amplitude data, collected during the baseline HIRREM assessment, and during subsequent HIRREM sessions. For similar

locations, eye states, and frequencies, we expect to see improved balance and reduced hyperarousal.

• RPQ for those with TBI. We expect to see reduced scores.

Research Design and Method:

Overview:

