This will be an open label, single site, pilot, clinical research study. Up to 40 active duty military personnel, or recent Veterans, age 18 or older, who have been diagnosed with PTSD, have received treatment for, are referred by military medical personnel for, or have active symptoms of militaryrelated traumatic stress, with or without mild TBI, will be recruited to receive up to 24 HIRREM sessions over 2 weeks. For those who self-refer, and do not have a prior diagnosis or treatment for PTSD, active symptoms will be identified by a screening PCL-M score of 50 or greater. Recruitment of 40 participants will allow us to achieve the goal of 36 participants to complete the intervention, allowing for the possibility of dropouts. The primary outcome will be differential change in the PCL-M from baseline to completion of HIRREM sessions. Secondary measures include the Insomnia Severity Index (ISI), the Center for Epidemiological Studies Depression Scale (CES-D), an anxiety measure (GAD-7), a quality of life measure (EQ-5D), an autonomic symptom measure (Compass 31), and a daily sleep diary, as well as physiological measures including heart rate (HR), and blood pressure (BP), with calculation of heart rate variability measures (HRV), and baroreflex sensitivity (BRS). Functional measures will include reaction time (drop-stick paradigm), and grip strength (hydraulic dynamometer), and analysis of brain patterns. If there is a history of TBI, a Rivermead Post-Concussion Symptoms Questionnaire (RPQ) will be added. There will be pre- and post-intervention data collection for all measures (baseline, V1, and at completion of HIRREM sessions, V2). Self-report measures will also be repeated by phone at 1, 3, and 6 months after completion of sessions (V3, V4, and V5 respectively). The online sleep diary will be maintained from V1 until V3. A brainwave assessment will be obtained at V1.

Participants/Subjects

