Heart rate is measured as beat-to-beat intervals (RRI) recorded by pulse-wave recording, and will be analyzed using custom software developed by Biopac. Data can be loaded and viewed, and a subset of the data can be selected to avoid artifacts during device placement or removal. Outlier identification is performed by determining all inter-beat intervals which demonstrate a 30% difference from the mean of the previous four samples. Such outliers are removed from the data set. HRV statistics that are generated include mean, variance, SDNN, RMSSD, pNN50, VLF, LF, HF, TP, LF/HF, sample

Version 1.0 10/06/2017

rpq

asymmetry, sample entropy, and coherence. All of the algorithms for computation of these parameters are derived from information or source code from the Physionet archive. Data are saved to Excel spreadsheets for further statistical analysis by study team members.

b) Blood Pressure (BP)

Blood pressure (BP) measurements will be taken with a finger cuff on two fingers of the left hand while lying down on an examination table.

Functional Measures:

Reaction Time

Reaction time testing will be measured by a drop-stick, clinical reaction time apparatus. It is constructed from a meter stick covered in the friction tape with gradations. The modified meter stick is fixed to a weighted rubber cylinder. The apparatus is placed between the thumb and index finger of the subject and released at a random time during a countdown. The subject catches the apparatus and the distance fallen is converted to reaction. Following two practice trials, subjects perform eight trials, and a mean distance value is used for analysis. This simple clinical measure has been evaluated by Eckner et al, and demonstrated utility in testing comparable to computerized testing methods²⁸. ⁴⁴

Grip Strength

Grip strength will be evaluated using a hydraulic hand dynamometer (Baseline Hydraulic Hand Dynamometer). The greatest force generated during three trials will be used for analysis²⁹.⁴⁵

Brain Pattern Analysis

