The proprietors of HIRREM have repeatedly observed that EEG asymmetries in the temporal lobes (specifically at T3 and T4 in the 10-20 International System for EEG correspond to autonomic dysfunction. When T4 signals are dominant to T3 signals a sympathetic state is favored which is manifested as symptoms of anxiety, cardiovascular over-drive, and hyperarousal. When T3 signals are excessively dominant to T4 signals a parasympathetic state is favored which is manifested as symptoms of emotional numbness, cardiovascular underactivity, GI dysfunction, and under-arousal. Lateralization of autonomic activity is not a novel finding, it is in accord with a number of previously published studies which support a hypothesis of autonomic lateralization⁴⁶.

EEG balance at T3 and T4 suggests autonomic balance and benefit, and our preliminary results suggest that utilization of HIRREM at T3 and T4 has demonstrated success in ameliorating symptoms associated with autonomic disruption^{31,47} Preliminary data also demonstrate correlation between a T3/T4 temporal asymmetry score and objective physiological changes reflective of autonomic signaling to the heart at the baseline assessment (AAN T3/T4 2013

poster). Reduction in the sum of high frequency amplitudes at T3/T4 (reduced hyperarousal), has also been observed in subjects with hot flashes⁴⁸. Comparison of such activity at T3 and T4 over time will provide objective physiological outcome data regarding the effect of HIRREM on autonomic balance and function.

5) Statistical Analysis

Data will be analyzed using the most recent versions of SAS (SAS Institute, Inc., Cary, NC) or the R Statistical Computing Environment. Histograms and descriptive statistics will be examined to evaluate the distribution of study outcomes. Because this proposal is designed to estimate effect sizes for future randomized trials, analyses will primarily consist of providing point estimates of effect size for each outcome along with corresponding 95% Cls. Given that outcomes will be collected at multiple follow-up time points (V2, V3, and V4), effect estimates will be based on generalized linear models, which can accommodate within-subject correlations due to repeated assessment over time. Critically, estimates produced from this pilot study will need to be used cautiously for planning future research, as it is well known that estimates from small sample sizes tend to be upwardly biased (overestimated effect sizes, underestimated variability⁵³.

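### Reaction time is to be analysed as mean drop distance, which mixes mean speed with trial-to-trial variability; each trial should be converted to time before averaging

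*Combined protocol and SAP*

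**What the plan says.** Under Secondary Objectives, the outcome is a time: "Reaction time, as evaluated by a drop-stick, clinical reaction time apparatus. We expect to see improved reaction time". The Reaction Time paragraph under Functional Measures describes the measurement. It first states: "The subject catches the apparatus and the distance fallen is converted to reaction". The sentence defining the analysed variable follows at once: "Following two practice trials, subjects perform eight trials, and a mean distance value is used for analysis".

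No conversion formula is given. The text does not say whether conversion comes before or after averaging, or whether the result is reported in centimetres or milliseconds.

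On timing, the Overview says: "There will be pre- and post-intervention data collection for all measures (baseline, V1, and at completion of HIRREM sessions, V2"). The later telephone contacts collect self-report measures only, so reaction time has one value before and one after the intervention. The Statistical Analysis section says that "analyses will primarily consist of providing point estimates of effect size for each outcome along with corresponding 95" per cent confidence intervals, to inform later randomised trials.

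**The concern.** The objective is reaction time, but the only sentence defining the analysed variable names distance. A dropped stick falls a distance proportional to the square of the time before it is caught. Averaging distances therefore averages squared times, so slow catches get extra weight and the result depends on how variable the eight catches are as well as how fast they are on average.

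This is relevant because the study has a single arm. If participants become more consistent with the apparatus by V2, mean distance falls even when mean speed has not changed. The shift is in the direction the protocol expects and no control group would reveal it. The estimate and its interval would then be carried into planning as a reaction-time effect.

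**Working it through.** The plan gives no mean, SD, effect or power for reaction time, so there is no figure of its own to reproduce.

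**Inputs from the protocol.** Eight scored trials after two practice trials (Reaction Time paragraph); measurement at V1 and V2; 36 expected completers (Overview: "Recruitment of 40 participants will allow us to achieve the goal of 36 participants to complete the intervention").

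**Assumed inputs.** Mean reaction time 200 ms; within-person trial SD 20 to 50 ms; g = 981 cm/s².

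**Step 1: what mean distance measures.** With d = g·t²/2, the expected mean distance is (g/2)·(μ² + s²), where μ is a person's mean time and s the trial SD. At μ = 0.200 s and s = 0, this is 490.5 × 0.04 = 19.62 cm. At s = 0.030 s it is 490.5 × (0.04 + 0.0009) = 20.06 cm, of which the variance term is 0.0009/0.0409 = 2.2%.

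**Step 2: converting the mean afterwards.** Applying sqrt(2d/g) to the mean distance gives sqrt(μ² + s²), not μ. At 200 ms the excess is 1.0, 2.2, 4.0 and 6.2 ms for s = 20, 30, 40 and 50 ms. The variance term remains.

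**Step 3: change in variability alone, with mean time fixed at 200 ms.**

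| Trial SD, V1 to V2 | Fall in mean distance, (g/2)(s₁² − s₂²) | Apparent gain after converting the mean |
|---|---|---|
| 30 to 20 ms | 490.5 × 0.0005 = 0.25 cm | 202.24 − 201.00 = 1.2 ms |
| 40 to 20 ms | 490.5 × 0.0012 = 0.59 cm | 203.96 − 201.00 = 3.0 ms |
| 50 to 20 ms | 490.5 × 0.0021 = 1.03 cm | 206.16 − 201.00 = 5.2 ms |

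If each trial is converted first, the expected gain is zero in every row.

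**Step 4: effect on the estimate.** A simulation used n = 36, eight trials per visit and 3,000 runs per scenario. It assumed subject means of 210 ms (SD 25 ms) and individual changes with SD 10 ms. The last column is the share of 95% intervals for the mean change that exclude zero. Each cell reads: per-trial times / mean distance / mean distance converted afterwards.

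| Trial SD, V1 to V2 | True mean gain | Mean standardised effect | Intervals excluding zero |
|---|---|---|---|
| 30 to 30 ms | 10 ms | 0.57 / 0.55 / 0.57 | 90% / 88% / 90% |
| 30 to 30 ms | 0 | 0.00 / −0.01 / 0.00 | 5% / 5% / 5% |
| 30 to 20 ms | 0 | 0.00 / 0.06 / 0.06 | 5% / 6% / 7% |
| 40 to 20 ms | 0 | 0.00 / 0.14 / 0.14 | 4% / 11% / 11% |
| 50 to 20 ms | 0 | 0.00 / 0.22 / 0.21 | 5% / 25% / 23% |

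When trial SD is stable, the choice of scale makes almost no difference. When it falls, both distance-based versions pick up a gain that is not there.

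**The case against.** A reader might infer that the reported effect is not a reaction-time effect at all. The documents do not support that. The sentence before the definition says distance is converted, so a settled plan to report only centimetres cannot be assumed; what is clear is that scale and order are left open. Nor does the algebra support it. Distance rises steadily with time, and the correlation between t and t² across simulated subjects is 0.996. At constant trial SD the standardised effects nearly coincide.

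A reader might also infer that the estimate is useless for planning, or that it is inflated about twofold because a percentage change in distance is roughly double that in time. No percentage-change analysis is planned for this outcome, and a square root undoes the change of units. A later trial using the same apparatus could use the distance estimate directly. The Statistical Analysis section already urges caution with pilot estimates.

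Further points on the other side are fair. The 5.2 ms figure needs trial SD to fall from 50 to 20 ms, and nothing in the documents suggests so large a fall; the 30 to 20 ms case gives about 1.2 ms and intervals close to nominal. The two practice trials should limit familiarisation, though they may not remove it. Averaging distances may follow the cited evaluation of the drop-stick test, which is not available here, so departure from that procedure cannot be judged.

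What stands is narrower: as written, the analysed value depends on trial variability, converting the mean afterwards does not remove this, and a better summary of the same eight readings is available at almost no cost.

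**Conclusion.** The point holds as a minor, nearly free improvement. The protocol names reaction time as the outcome, specifies mean distance as the analysed value, and leaves the conversion undefined. The practical effect is negligible if within-person variability is the same at both visits. If variability falls, the apparent gain is about 1.2 to 5.2 ms at an assumed mean of 200 ms, for an assumed fall in trial SD to 20 ms from 30 to 50 ms. The algebra is certain. The size is not, since the documents give no reaction-time mean or trial SD.

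Only one secondary measure in an estimation pilot is affected; the PCL-M analysis is untouched. Per-trial conversion also leaves a separate limit in place: a real practice gain in mean speed cannot be told apart from an intervention effect on either scale without a control group.

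**What to change.** In the Reaction Time paragraph, replace the definition of the analysed value with: *each trial distance is converted to time, t = sqrt(2d/g), and the mean of the eight times (ms) is analysed.* This settles formula, order and unit together. The within-person SD of the eight times could be added as a descriptive summary, so that a change in consistency is reported as such.

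The cost is one line in data processing, with no new measurement. The addendum shows that participants had already been studied when this version was written. The formula can be applied to them retrospectively if their eight trial distances were stored, which the documents do not say. Where only a mean distance was kept, the report should say so, because the variance term cannot then be removed.
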